5.3. Medical History

Medical history will be collected at screening for disease-specific and general conditions (ie, conditions not specific to the disease being studied).

General medical history data will not be coded, but will be listed only.

A by-subject listing of disease-specific and general medical history will be provided by subject ID number in ascending order.

5.4. Prior Anticancer Therapy

Number of prior regimens and time since the completion of last regimen will be summarized by study group and dose level using descriptive statistics based on the FAS. A partial completion date will be imputed as follows:

- If day and month are missing but year is available, then the imputed day and month will be 01 Jan.
- If day is missing but the month and year are available, then the imputed day will be the first day of the month.
- Partial date will not be imputed if the year is missing.

The regimens and prior therapies that the subjects received will be summarized. The last regimen subjects received prior to study entry and the best response to the last regimen will be summarized.

Number of subjects who received prior radiation therapy will be listed.

6. EFFICACY ANALYSES

6.1. Efficacy Endpoint

6.1.1. Definition of Efficacy Endpoints

6.1.1.1. Progression-free Survival

Progression-free survival is defined as the interval from first dosing date of study drug to the earlier of the first documentation of definitive disease progression or death from any cause. Definitive disease progression is determined based on RECIST v1.1 for solid tumors {Eisenhauer 2009} or Cheson Criteria {Cheson 2007} for lymphoma or PCWG2 for prostate cancer.

The date of definitive progression will be the time point at which progression is first identified by relevant radiographic, imaging, or clinical data. Data will be censored on the date of last adequate tumor assessment for subjects:

- who do not have documented progression or die, or
- who start new anticancer therapy before documented progression, or
- who start new anticancer therapy before death without documented progression, or
- who have ≥ 2 consecutive missing tumor assessments before documented progression, or
- who have ≥ 2 consecutive missing tumor assessments before death without documented progression

If a subject does not have a baseline tumor assessment, then PFS will be censored at Study Day 1, regardless of whether or not definitive progression or death has been observed.

When the date of initiation of anticancer therapy other than the study treatment is incomplete or missing, the following algorithm will be followed:

- If the day is missing but the month and year are available, then the imputed day will be the last day of the month.
- If day and month are missing but year is available, then the imputed day and month will be 01Jan or the last day of the month for the last adequate disease assessment if they have the same year, whichever is later.

6.1.1.2. Overall Response Rate

Overall response rate is defined as the proportion of subjects who achieve best overall response (BOR) of complete response (CR) or partial response (PR) during study. The response definition of each response category is based on RECIST v1.1 for solid tumors, and Cheson Criteria for lymphoma. Subjects, who do not have sufficient baseline or on-study tumor status information to be adequately assessed for response status (ie, those with best overall response of not evaluable [NE]) or received anticancer therapy other than the study treatment prior to achieving CR or PR, will be considered as nonresponders and will be included in the denominators in calculations of response rates.

6.1.2. Analysis Methods for Efficacy Endpoints

6.1.2.1. Progression-free Survival

Progression-free survival based on investigators' assessments will be summarized using descriptive statistics by study group and dose level.

6.1.2.2. Overall Response Rate

Overall response rate based on investigators' assessments will be calculated along with its 95% CIs based on exact method. In the analyses of ORR, the BOR will be summarized by study group, dose level, and each response category as CR, PR, SD, PD, and NE.

7. SAFETY ANALYSES

7.1. Adverse Events and Deaths

7.1.1. Adverse Event Dictionary

Clinical and laboratory AEs will be coded using the current version of MedDRA. System organ class (SOC), high-level group term (HLGT), high-level term (HLT), preferred term (PT), and lower-level term (LLT) will be provided in the AE dataset.

7.1.2. Adverse Event Severity

Adverse events are graded by the investigator as Grade 1, 2, 3, 4, or 5 according to CTCAE Version 4.03. The severity grade of events for which the investigator did not record severity will be categorized as “missing” for tabular summaries and data listings. The missing category will be listed last in summary presentation.

7.1.3. Relationship of Adverse Events to Study Drug

Related AEs are those for which the investigator selected “Related” on the AE CRF to the question of “Related to Study Treatment.” Relatedness will always default to the investigator’s choice, not that of the medical monitor. Events for which the investigator did not record relationship to study drug will be considered related to study drug for summary purposes. However, by-subject data listings will show the relationship as missing.

7.1.4. Serious Adverse Events

Serious adverse events (SAEs) will be identified and captured as SAEs if the AEs met the definitions of SAEs that were specified in the study protocol. SAEs captured and stored in the clinical database will be reconciled with the SAE database from the Gilead Drug Safety and Public Health Department before data finalization.

7.1.5. Treatment-Emergent Adverse Events

7.1.5.1. Definition of Treatment-Emergent Adverse Events

Treatment-emergent adverse events (TEAEs) are defined as 1 or both of the following:

- Any AEs with an onset date on or after the study drug start date and no later than 30 days after permanent discontinuation of study drug
- Any AEs leading to premature discontinuation of study drug.

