6. STUDY PROCEDURES

The study procedures to be conducted for each subject enrolled in the study are presented in tabular form in [Appendix 2](#) and described in the text below.

The investigator must document any deviation from protocol procedures and notify the sponsor or contract research organization (CRO).

Safety and tolerability assessments will include regular monitoring of AEs, changes from baseline in laboratory variables, physical examinations, vital signs, and special safety assessment like ECGs.

From the time of obtaining informed consent through the first administration of investigational medicinal product, record all serious adverse events (SAEs), as well as any non-serious AEs related to protocol-mandated procedures on the AEs electronic case report form (eCRF). All other untoward medical occurrences observed during the Screening period, including exacerbation or changes in medical history are to be captured on the medical history eCRF. See Section 7 for additional details.

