7.2.2. Assessment of Severity

The severity of AEs will be graded using the CTCAE, Version 4.03 ([Appendix 6](#)). For each episode, the highest severity grade attained should be reported.

If a CTCAE criterion does not exist, the investigator should use the grade or adjectives: Grade 1 (mild), Grade 2 (moderate), Grade 3 (severe), Grade 4 (life-threatening), or Grade 5 (fatal) to describe the maximum intensity of the AE. For purposes of consistency with the CTCAE, these intensity grades are defined in [Table 7-1](#).

Table 7-1. Grading of Adverse Event Severity

Grade	Adjective	Description
Grade 1	Mild	Sign or symptom is present, but it is easily tolerated, is not expected to have a clinically significant effect on the subject's overall health and well-being, does not interfere with the subject's usual function, and is not likely to require medical attention.
Grade 2	Moderate	Sign or symptom causes interference with usual activity or affect clinical status, and may require medical intervention.
Grade 3	Severe	Sign or symptom is incapacitating or significantly affects clinical status and likely requires medical intervention and/or close follow-up.
Grade 4	Life-threatening	Sign or symptom results in a potential threat to life.
Grade 5	Fatal	Sign or symptom results in death.

The distinction between the seriousness and the severity of an AE should be noted. Severe is a measure of intensity; thus, a severe reaction is not necessarily a serious reaction. For example, a headache may be severe in intensity, but would not be classified as serious unless it met 1 of the criteria for serious events listed in Section 7.1.2.

7.3. Investigator Requirements and Instructions for Reporting Adverse Events and Serious Adverse Events to Gilead

7.3.1. Requirements for Collection Prior to Study Drug Initiation:

After informed consent, but prior to initiation of study medication, the following types of events should be reported on the eCRF: all SAEs and AEs related to protocol-mandated procedures.

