8.6.2. Adverse Events

All AEs will be listed. The focus of AE summarization will be on treatment-emergent AEs. A treatment-emergent AE is defined as an AE that occurs or worsens in the period from the first dose of study drug (GS-5829, exemestane or fulvestrant) to 30 days after the last dose of study drug.

AEs will be coded using the Medical Dictionary for Regulatory Activities (MedDRA <http://www.meddrasso.com>) with descriptions by System Organ Class (SOC), High-Level Group Term, High-Level Term, Preferred Term, and Lower-Level Term. The severity of AEs will be graded by the investigator according to the CTCAE, Version 4.03, whenever possible. If a CTCAE criterion does not exist for a specific type of AE, the grade corresponding to the appropriate adjective will be used by the investigator to describe the maximum intensity of the AE: Grade 1 (mild), Grade 2 (moderate), Grade 3 (severe), Grade 4 (life threatening), or Grade 5 (fatal). The relationship of the AE to the IP will be categorized as related or unrelated.

TEAEs will be summarized by dose level. Summary tables will be presented to show the number of subjects reporting treatment-emergent AEs by severity grade and corresponding percentages. A subject who reports multiple treatment-emergent AEs within the same Preferred Term (or SOC) is counted only once for that Preferred Term (or SOC) using the worst severity grade. AE descriptions will be presented by decreasing frequency for a given SOC and Preferred Term. Separate listings and summaries will be prepared for the following types of treatment emergent AEs:

- Study-drug-related (GS-5829, exemestane or fulvestrant) AEs
- AEs that are Grade ≥ 3 in severity
- AEs leading to study drug (GS-5829, exemestane or fulvestrant) interruption and/or dose modification
- AEs leading to study drug (GS-5829, exemestane or fulvestrant) discontinuation
- SAEs

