7.7. Changes From Protocol-Specified Safety Analyses

There are no deviations from the protocol-specified safety analyses.

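### SAP 7.1.5.1 drops the worsening limb of the protocol's treatment-emergent AE definition, while SAP 7.7 declares no deviations

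*SAP*

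**What the plan says.** Protocol 8.6.2 sets the definition: "A treatment-emergent AE is defined as an AE that occurs or worsens in the period from the first dose of study drug". Study drug there means any of GS-5829, exemestane and fulvestrant, and the window closes 30 days after the last dose. An event can therefore qualify by starting in the window or by getting worse in it.

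SAP 7.1.5.1 gives two routes. The first is by onset date: "Any AEs with an onset date on or after the study drug start date and no later than 30 days after permanent discontinuation". The second is by consequence: "Any AEs leading to premature discontinuation of study drug". Neither mentions worsening. SAP 7.1.5.2, on incomplete dates, also works from onset and stop dates alone.

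SAP 7.7 then states: "There are no deviations from the protocol-specified safety analyses".

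Three protocol rules decide which records could fall between the two definitions:

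- **Section 6 (and 7.3.1), before first dose.** Only SAEs and AEs related to protocol procedures go on the AE form. Other screening occurrences, "including exacerbation or changes in medical history are to be captured on the medical history eCRF", are kept apart.
- **Section 7.1.1.** A pre-existing event that increases in severity during the study is itself an AE.
- **Section 7.2.2, on grading.** "For each episode, the highest severity grade attained should be reported".

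**The concern.** Characterizing safety and tolerability is a primary objective. The SAP builds its TEAE tables on this definition: Grade 3 or higher, GS-5829-related, serious, and leading to interruption, dose reduction or death (7.1.6.1). The AEs of interest are summarized in the same way (7.1.7.2).

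An AE that was present before dosing and became worse on drug is one the protocol asks to be counted. Under an onset-date rule it can disappear from these tables without anyone having decided that it should. Because SAP 7.7 reports no change, a reader of the study report would assume that the protocol definition had been applied.

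Haemorrhage shows where this could matter. It is an AE of interest, and its term list in SAP Appendix 3 includes puncture-site, catheter-site and post-procedural haemorrhage. Events of that kind can follow a screening venipuncture or biopsy.

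**Working it through.** The plan gives no figure on this point to reproduce. The check compares the two definitions for one type of event: it starts between consent and first dose, worsens after first dose, and does so within 30 days of the last dose.

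| How the event is recorded | Protocol 8.6.2 | SAP 7.1.5.1 |
|---|---|---|
| (a) SAE or procedure-related AE already on the AE form, kept as one record with pre-dose onset, not leading to discontinuation | TEAE | Not a TEAE |
| (b) As (a), but leading to discontinuation | TEAE | TEAE, by the second route |
| (c) As (a), but the worsening is entered as a new AE dated on drug | TEAE | TEAE |
| (d) Medical-history condition whose worsening is entered as an AE dated on drug | TEAE | TEAE |
| (e) As (d), but entered with the original screening date | TEAE | Not a TEAE, unless it leads to discontinuation |

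The definitions part in (a) and (e). Which row applies depends on the onset date that the site enters when an existing event worsens, and neither document gives that rule. Protocol 7.3.3 and 7.3.4 refer to eCRF completion guidelines, which are not part of the documents. Protocol 6.1.9 is looser than Section 6, since it sends any AE after consent to the eCRF. If sites followed 6.1.9, more events could fall in (a).

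**Size per affected subject.** Inputs: 33 subjects enrolled (SAP 1.3), and cohorts of 3 to 6 (Protocol 3.2). TEAE tables use the Full Analysis Set (SAP 7.1.6), so the overall figure assumes that all 33 were dosed. If the subject has no other event in that table row, the row moves by 100 × 1/n percentage points:

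- Overall: 100 × 1/33 = 3.0
- Cohort of 6: 100 × 1/6 = 16.7
- Cohort of 3: 100 × 1/3 = 33.3

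If the subject already counts in the row through another event, the change in that row's total is zero.

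**What does not move.**

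- The DLT listing (SAP 7.1.7.1) does not use the TEAE definition, so the primary endpoint is untouched.
- SAP 7.1.6.1 lists every AE with a treatment-emergent flag. An affected event stays in the report but carries the wrong flag.
- Treatment-emergent laboratory abnormalities keep a worsening rule of at least one grade from baseline (SAP 7.2.2.1), in line with Protocol 8.6.3. The SAP thus keeps worsening for laboratory data and omits it for AEs, without giving a reason.

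**The case against.** The strongest reply is that the loss is possible but not shown. A reader might infer from Protocol 7.2.2 that each episode is held as one row and keeps its first onset date. The section does not say that. It asks for the highest grade and is silent on rows, record splitting and dates. Nor does the worsening rule in Protocol 7.1.1 apply only to medical-history items. A site could properly enter the worsening as a new AE dated on drug, and the SAP would count it.

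A reader might also infer that every screening event that worsens on drug is lost. The documents do not support that either. Most non-serious screening events are never AE records, and events that end treatment are counted by the second route. Exclusion criteria 1 and 4 should also make an unresolved SAE at first dose uncommon.

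All of this stands, and it limits the point to row (a) and, depending on site practice, row (e). It does not remove the difference between Protocol 8.6.2 and SAP 7.1.5.1, and it does not make the statement in SAP 7.7 correct. If the recording rule turns out to be a new dated record for each worsening, the difference has no numerical effect, but the SAP should then say so.

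**Conclusion.** The point holds as a definitional mismatch with a narrow possible undercount. The SAP's definition is stricter than the protocol's, and 7.7 is wrong to report no change. The undercount is confined to screening-onset SAEs and procedure-related AEs that worsen on drug without leading to discontinuation and are kept with a pre-dose onset date. It is wider only if sites follow Protocol 6.1.9 or carry the original date into a later AE entry.

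The number of subjects cannot be worked out from the documents and may be zero. A reader might want to put a range on it, but there is no basis for one. Nor should the point be read as a threat to the DLT endpoint or as events vanishing from the report.

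The conclusion assumes that the protocol text supplied matches the amendment 6 on which the SAP says it is based. That cannot be confirmed, because the title pages are missing. The point is minor, but it bears on a primary objective and is cheap to put right.

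**What to change.** 1. Add a third route to SAP 7.1.5.1: any AE with onset before first dose that worsens between the first dose of any study drug (GS-5829, exemestane or fulvestrant) and 30 days after the last. Name all three drugs, as the protocol does. Exemestane may start before Cycle 1 Day 1, so anchoring on GS-5829 alone would create a new departure. Keep the 30-day limit.
2. State that on-drug worsening is identified by the date of worsening, taken from a new AE record or from SAE follow-up data, which SAP 7.1.4 already reconciles with the safety database. That reconciliation covers serious events only. A non-serious procedure-related AE would need a separate dated record or a data query.
3. Correct SAP 7.7.

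If the sponsor prefers the onset-only rule, the minimum is to declare it in 7.7 as a change from Protocol 8.6.2.

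The cost is a few sentences, a small derivation and data-review step, and possibly slightly higher TEAE counts.

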7.1.5.2. Incomplete Dates

If the onset date of the AE is incomplete and the AE stop date is not prior to the first dosing date of study drug, then the month and year (or year alone if month is not recorded) of onset determine whether an AE is treatment emergent. The event is considered treatment emergent if both of the following 2 criteria are met:

- The AE onset is the same as or after the month and year (or year) of the first dosing date of study drug, and
- The AE onset date is the same as or before the month and year (or year) of the date corresponding to 30 days after the date of the last dose of study drug

An AE with completely missing onset and stop dates, or with the onset date missing and a stop date later than the first dosing date of study drug, will be considered to be treatment emergent. In addition, an AE with the onset date missing and incomplete stop date with the same or later month and year (or year alone if month is not recorded) as the first dosing date of study drug will be considered treatment emergent.

If the onset of the AE is incomplete and needs to be imputed, the following algorithm will be followed:

- If the day is missing but the month and year are available, then the imputed day will be the first day of the month or the first dosing date if they have the same month and year, whichever is later.
- If the day and month are missing but year is available, then the imputed day and month will be 01Jan or the first dosing date if they have the same year, whichever is later.

7.1.6. Summaries of Adverse Events and Deaths

Treatment-emergent AEs will be summarized based on the FAS.

7.1.6.1. Summaries of AE incidence by Severity

The number and percentage of subjects who experienced at least 1 TEAE will be provided and summarized by SOC, PT, dose level, and study group. For other AEs described below, summaries will be provided by SOC, PT, maximum severity, dose level, and study group:

- TEAEs
- TEAEs of Grade 3 or higher
- TE GS-5829-related AEs
- TE GS-5829-related AEs of Grade 3 or higher

- TE SAEs
- TE GS-5829-related SAEs
- TEAEs leading to premature discontinuation of GS-5829
- TEAEs leading to death
- TEAEs leading to temporary interruption of GS-5829
- TEAEs leading to dose reduction of GS-5829

A brief, high-level summary of AEs described above will be provided by study group and dose level and by the number and percentage of subjects who experienced the above AEs.

Multiple events will be counted only once per subject in each summary. Adverse events will be summarized and listed first in alphabetic order of SOC and HLT within each SOC (if applicable), and then by PT in descending order of total frequency within each SOC. For summaries by severity grade, the most severe grade will be used for those AEs that occurred more than once in an individual subject during the study.

In addition to the above summary tables, TEAEs, TEAEs of Grade 3 or higher, TE treatment-related AEs, and TE SAEs will be summarized by PT only in descending order of total frequency.

In addition, data listings will be provided for the following:

- All AEs, indicating whether the event is treatment emergent
- All AEs of Grade 3 or higher
- SAEs
- Deaths
- AEs leading to death
- AEs leading to premature discontinuation of GS-5829
- AEs leading to temporary interruption of GS-5829
- AEs leading to dose reduction of GS-5829

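### For Groups 2A and 2B the SAP limits treatment-change AE outputs to GS-5829 and labels related AEs as GS-5829-related, although the protocol covers any study drug and SAP 7.7 declares no deviations

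*SAP*

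**What the plan says.** Protocol 8.6.2 fixes the form of output: "Separate listings and summaries will be prepared for the following types of treatment emergent AEs". Three of the types that follow carry the same parenthesis:

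- "Study-drug-related (GS-5829, exemestane or fulvestrant) AEs"
- "AEs leading to study drug (GS-5829, exemestane or fulvestrant) interruption and/or dose modification"
- "AEs leading to study drug (GS-5829, exemestane or fulvestrant) discontinuation"

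SAP 7.1.6.1 plans summaries by SOC, PT and maximum severity. Three concern relatedness, and all name GS-5829: related AEs, "TE GS-5829-related AEs of Grade 3 or higher", and related SAEs. Three concern treatment changes, and these also name only GS-5829: "TEAEs leading to premature discontinuation of GS-5829", plus temporary interruption and dose reduction. The three matching listings have the same limit. One further table, by PT only, refers to treatment-related AEs and names no drug.

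On the source of relatedness, SAP 7.1.3 says: "Related AEs are those for which the investigator selected" the related option on a CRF question about study treatment. Missing answers count as related.

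SAP 7.7 closes the safety section: "There are no deviations from the protocol-specified safety analyses".

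**The concern.** Safety and tolerability of GS-5829 combined with exemestane or fulvestrant is a primary objective in Protocol Section 2 and SAP 1.1. The SAP plans no formal testing (3.5), so the descriptive AE tables are a main part of the evidence on that objective.

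In Groups 2A and 2B the regimen has two drugs. If the partner drug is stopped or held because of an AE and GS-5829 continues, that is a tolerability event for the combination. The protocol's scope counts it and the SAP's does not. The relatedness label raises a separate issue: in a combination group it claims attribution to one drug, while the field cited in 7.1.3 asks about the treatment as a whole. Because 7.7 says nothing has changed, a reader of the study report would not know that the scope is narrower than the protocol's.

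**Working it through.** The plan gives no figure to reproduce. The check sets the two texts side by side.

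| AE type | Protocol 8.6.2 scope | SAP 7.1.6.1 summaries | SAP 7.1.6.1 listings |
|---|---|---|---|
| Related | Any of the three drugs | GS-5829 by label in three SOC/PT/severity tables; no drug named in the PT-only table | None separate; by-subject listings show the relationship (7.1.3) |
| Interruption or modification | Any of the three drugs | GS-5829 only (interruption; dose reduction) | GS-5829 only (both) |
| Discontinuation | Any of the three drugs | GS-5829 only | GS-5829 only |

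**Count.** All 3 protocol categories that name the partner drugs are narrowed, at least by label, in the SAP's main tables. All 3 treatment-change summaries and all 3 treatment-change listings name GS-5829 only. The high-level AE summary in 7.1.6.1 is built from the same categories and inherits the limit. SAP 7.7 declares 0 deviations.

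**Is GS-5829 merely shorthand for study drug?** The SAP uses both terms. Section 7.1.5.1 defines treatment-emergent AEs by reference to study drug, and 7.1.6.1 then switches to GS-5829 by name. The exposure section follows the same pattern: Protocol 8.6.1 asks for doses, modifications and interruptions for all three drugs, while SAP 4.2 covers GS-5829 only. The plain reading is a narrower scope.

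**Can a partner-only action occur?** Protocol 6.7 leaves it to the investigator whether to withhold the drug to which the AE is not attributed. Attribution to one drug, and action on one drug alone, are therefore foreseen.

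**Which events are affected?** An AE that stops or holds GS-5829, with or without the partner drug, is captured by the SAP. Only AEs leading to action on exemestane or fulvestrant alone are missing. Groups 1 and 3 receive a single agent and are unaffected.

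**Illustration.** Group 2 escalates in cohorts of 3 to 6 subjects (Protocol 3.2). Suppose one subject discontinues only the partner drug because of an AE.

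- Cohort of 3: protocol scope 1/3 = 33%; SAP scope 0/3 = 0%.
- Cohort of 6: protocol scope 1/6 = 17%; SAP scope 0/6 = 0%.

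The documents do not say that this happened or how often to expect it.

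**The case against.** The case on the other side has four parts.

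1. *The protocol's parenthesis is pooled.* A reader might infer that the protocol promised separate exemestane and fulvestrant tables and that the SAP dropped them. The text does not support this: it defines AE types across any study drug. The objection stands, and the point is about lost coverage of partner-drug actions, not missing per-drug tables.

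2. *Relatedness may differ only in name.* Protocol 8.6.2 plans one binary attribution to the IP, and SAP 7.1.3 cites one CRF question. If that field feeds the GS-5829-related tables, their counts already equal the protocol's pooled content. A reader might infer that partner-drug-related AEs are omitted or that the counts are wrong. The documents do not show this, because the SAP never says how the GS-5829 label is assigned and the CRF is not supplied. What remains is a label that the cited field does not support, used beside a PT-only table with a different label.

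3. *No AE disappears.* The overall TEAE, Grade 3 or higher, SAE and death summaries are not drug-specific, and all AEs are listed. The disposition table (SAP 4.1) refers to study drug without naming one, so it may count some partner-drug stops. A reader might infer that partner-drug toxicity is lost from the report; that is too strong. What the treatment-change outputs miss is the link between an AE and the action taken on the partner drug.

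4. *The primary endpoint is untouched.* It is DLT incidence, and a Group 2 DLT must be possibly related to GS-5829 (Protocol 3.2). This also stands, but the primary objective covers tolerability of the combination more broadly than DLTs.

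None of the four reconciles the treatment-change outputs in SAP 7.1.6.1 with Protocol 8.6.2, or makes the statement in 7.7 correct.

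**Conclusion.** The point holds for treatment changes. SAP 7.1.6.1 restricts all three summaries and all three listings to GS-5829 where the protocol covers any study drug, so SAP 7.7 is wrong as written. The gap is confined to Groups 2A and 2B and to AEs leading to action on the partner drug alone. How many such AEs there are cannot be told from the documents: the SAP reports 33 subjects enrolled in all and gives no count of partner-drug stops. One event would move a cell by 17 to 33 percentage points in cohorts of 6 and 3 respectively.

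For relatedness, the documents support only a labelling problem and an unstated derivation.

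Two assumptions apply. First, the supplied protocol and the one the SAP follows agree on this section. The SAP cites amendment 6, the supplied protocol's amendment number is not visible, and the subject caps differ (160 in Protocol 8.9, 120 in SAP 1.3), although the schedules of assessments match. Second, the AE CRF records action taken on the partner drug, which the documents do not show.

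**What to change.** 1. In SAP 7.1.6.1, for Groups 2A and 2B, widen the interruption, dose-modification and discontinuation summaries and listings to the protocol's pooled scope of GS-5829, exemestane or fulvestrant.
2. Label the relatedness tables study-treatment-related, consistently with the PT-only table, unless the CRF records attribution for each drug. If it does, state in 7.1.3 how GS-5829-related is derived.
3. Treat separate partner-drug tables as optional, and plan them only if the CRF has the fields.
4. Correct Section 7.7. If the CRF cannot support the pooled outputs, declare the narrowing there and give the reason. If the SAP is already final, SAP Section 1 provides for recording the change in the study report.

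The cost is a wider selection rule for a few descriptive tables and listings, some relabelling and one corrected paragraph, provided the CRF holds the action taken on each drug. If it does not, the cost is the paragraph and the relabelling.
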